1. PURPOSE OF THE STUDY

a. Brief Summary

The purpose of this study is to compare effectiveness of duloxetine and desipramine in (1) decreasing pain, (2) improving function, (3) improving depression and (4) decreasing pain interference in patients with chronic pain. We will also compare compliance of patients with these two medications. We will apply a novel point of care randomization method which allows integration of randomized comparative effectiveness research with patient care.

b. Objectives

The importance of the proposed research has two aspects: 1) it establishes how pragmatic clinical trials can be integrated with patient care. This will lead to numerous more trials in future that can generate more evidence and direction for medical practice in perioperative and pain medicine; 2) it will determine if either a tricyclic antidepressant or a serotonin norepinephrine reuptake inhibitor is superior in treating patients with chronic pain. The subgroup analysis proposed will provide information about characteristics of patients who respond to these medications differently.

c. Rationale for Research in Humans

The study is comparing effectiveness of duloxetine and desipramine in patients with chronic pain. Administration of these medications to human subjects is necessary for the purpose of the study.

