Comparing Effectiveness of Duloxetine and Desipramine in Patients With Chronic Pain: A Pragmatic Trial Using Point of Care Randomization

Statistical Analysis Plan

NCT03548454

Revised March 28, 2025

Statistical Analysis. The initial sample size calculation determined that 107 participants per group would provide 90% power to detect a one-unit between-group difference in the NRS pain score ($SD=2.25$) at $\alpha=0.05$. However, the study was prematurely stopped due to most referred patients having prior experience with duloxetine or, less frequently, desipramine. As a result, we enrolled 38 patients in the desipramine group and 48 in the duloxetine group. With this sample size, we could detect a difference of 1.37–1.58 in NRS pain reduction with 80–90% power.

Participants were eligible if they completed at least one survey before being assigned a study medication and at least one follow-up survey. The baseline assessment was defined as the most recent survey before treatment assignment. Participants without follow-up surveys or those lost to follow-up were excluded. The primary analysis followed modified intention-to-treat (ITT) principles. However, within the first day of treatment assignment, five individuals switched from desipramine to duloxetine. To account for these switches, a per-protocol (PP) analysis was conducted, categorizing individuals based on the medication they took. For consistency, survey data (research and clinical surveys) were evaluated up to 52 weeks post-baseline when available.

Baseline demographic and clinical characteristics were summarized using three comparative analyses. First, a “per-protocol” approach was applied to compare demographic and clinical characteristics between the desipramine and duloxetine groups. Second, differences were assessed between participants who completed the full course of medication and those who discontinued early. Third, participants who achieved a clinically meaningful ($\geq 30\%$) pain reduction were compared to those who did not. Categorical variables were analyzed using Pearson’s Chi-square or Fisher’s Exact tests, while continuous variables were assessed using t-tests or Mann-Whitney U tests depending on normality.

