Longitudinal changes in pain intensity, physical function, and psychological function were analyzed using linear mixed-effects models (LMMs). Dependent variables included pain intensity (average and worst), PROMIS Pain Interference, PROMIS Anxiety, PROMIS Depression, and PROMIS Physical Function (Upper Extremity, Mobility, and Composite) scores. The primary independent variables were medication group (desipramine vs. duloxetine) and its interaction with time (weeks since baseline) to assess differential treatment effects. Baseline pain intensity was included as a covariate. A random intercept for each participant accounted for within-subject correlations. Various model structures were evaluated using Akaike Information Criterion and Bayesian Information Criterion, with final models selected based on model fit and diagnostic assessments. Model fit was evaluated using residual plots, Q-Q plots, histograms, and Variance Inflation Factor analyses. Bonferroni correction was applied to account for multiple comparisons. LOESS (Locally Estimated Scatterplot Smoothing) predicted values with 95% confidence intervals were plotted to visualize longitudinal trends stratified by medication group.

Kaplan-Meier survival analysis was used to evaluate medication adherence over time, conducted separately for both the intention-to-treat and per-protocol analyses. Time to discontinuation was calculated as the number of days between treatment initiation and discontinuation. Participants who completed the full course of medication were censored at the maximum observed follow-up duration. Kaplan-Meier survival curves were generated for each medication group, and the log-rank test was used to compare groups with 95% confidence intervals. A Kaplan-Meier survival analysis was also conducted to compare the time to achieving a $\geq 30\%$ reduction in average pain intensity from baseline between medication groups. A binary indicator variable was created to determine whether a participant met the pain reduction threshold at any follow-up point, with time-to-event defined as the earliest occurrence of this reduction. Participants who did not achieve the threshold were censored at 52 weeks. Kaplan-Meier survival curves were plotted separately for desipramine and duloxetine, with the log-rank test used for group comparisons.

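### As written, the six PROMIS mixed models adjust for baseline pain but not for their own baseline score, which costs precision in the between-arm level comparison if week 0 is not a response

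*SAP*

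**What the plan says.** The mixed-model paragraph of the SAP's Statistical Analysis section covers eight outcomes with one description: "Dependent variables included pain intensity (average and worst), PROMIS Pain Interference, PROMIS Anxiety, PROMIS Depression, and PROMIS Physical Function", the last being three scores (upper extremity, mobility, composite). Two outcomes are pain ratings and six are PROMIS scores.

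The treatment terms are the same for all: "The primary independent variables were medication group (desipramine vs. duloxetine) and its interaction with time (weeks since baseline"). There is a random intercept per participant. The only baseline covariate named is in the sentence "Baseline pain intensity was included as a covariate". Average or worst pain is not specified.

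Earlier in the same section the SAP makes a pre-assignment survey a condition of analysis: "Participants were eligible if they completed at least one survey before being assigned a study medication and at least one follow-up survey". It then fixes which survey counts: "The baseline assessment was defined as the most recent survey before treatment assignment". It does not say whether that survey enters the models as a week-0 response. On the length of follow-up, "survey data (research and clinical surveys) were evaluated up to 52 weeks post-baseline when available".

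Protocol section 1a lists four effectiveness aims. The first is pain; the others are "2) improving function, (3) improving depression and (4) decreasing pain interference in patients with chronic pain".

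**The concern.** For average pain, baseline pain intensity is presumably the outcome's own baseline. For worst pain it is unclear which score is meant. For pain interference, anxiety, depression and the three function scores it is another variable, probably a weaker predictor of follow-up than the outcome's own earlier value.

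Five of these six models serve three of the protocol's four effectiveness aims; anxiety is not among those aims. Enrolment stopped at 86, against 214 (2 × 107) in the sample size calculation, and a Bonferroni correction applies, so precision is scarce. Medication group is one of the two primary model terms, so a level comparison is part of the plan even though no follow-up time is named for it.

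**Working it through.** **The plan's own figures.** With SD 2.25 and two-sided alpha 0.05 (sidedness assumed):

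- n per group = 2 × (1.960 + 1.282)² × 2.25² / 1² = 106.4, so 107, as stated.
- Detectable difference with 38 and 48 = (1.960 + z_power) × 2.25 × √(1/38 + 1/48). This is 1.37 at 80% power and 1.58 at 90%, as stated.

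These reproduce, but they are for NRS pain without covariate adjustment and say nothing about the PROMIS outcomes.

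**Inputs for the check.** From the documents: 38 and 48 patients, monthly surveys (Protocol 2a), data to 52 weeks, group × time with a random intercept. Assumed: outcome SD 1; equal correlation r among a PROMIS score's baseline and follow-ups; correlation q of baseline pain with that score; number of surveys uniform on 1–6 or 1–12, spaced 52/12 weeks. Cases (r, q): (0.5, 0.4), (0.6, 0.3) as central, (0.7, 0.2).

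**Formulae.** After adjustment for baseline pain, each follow-up has variance 1 − q² and each pair covariance r − q². After adjustment for own baseline these are 1 − r² and r − r². The standard error (SE) of the arm difference at a given week then follows by generalised least squares.

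A hand check for the mean of m surveys: let A = [1 + (m − 1)r]/m. The variance ratio, pain-only over own-baseline, is (A − q²)/(A − r²). For r = 0.6, q = 0.3, m = 6: A = 0.667, and 0.577/0.307 = 1.88. For m = 1: 0.91/0.64 = 1.42.

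**Results, week 0 not a response, 1–6 surveys** (SE pain-only / SE own-baseline; own-to-pain variance ratio from unrounded SEs):

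| r, q | Group term at time 0 | Week 13 | Week 26 |
|---|---|---|---|
| 0.5, 0.4 | 0.213 / 0.203; 0.904 | 0.160 / 0.145; 0.820 | 0.267 / 0.255; 0.914 |
| 0.6, 0.3 | 0.219 / 0.187; 0.730 | 0.180 / 0.137; 0.584 | 0.266 / 0.234; 0.772 |
| 0.7, 0.2 | 0.221 / 0.166; 0.563 | 0.194 / 0.125; 0.416 | 0.260 / 0.207; 0.634 |

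**1–12 surveys**, variance ratios in the same case order: week 13, 0.798, 0.549, 0.382; week 26, 0.803, 0.559, 0.394; week 52, 0.901, 0.739, 0.587.

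The central week-13 ratio corresponds to 1/0.584 = 1.71 times as many patients for the same precision.

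**Group-by-time term.** Central SE 0.0127 (pain-only) against 0.0124 SD per week (own baseline), with 1–6 surveys. A simulation with complete data at six visits gave a slope SE ratio of 1.000.

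**If week 0 is a response (1–6 surveys):**

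- One common baseline mean, arms free to differ afterwards: central SE 0.137 at week 13 and 0.234 at week 26, the same as own-baseline adjustment. Nothing is lost.
- Separate arm means at baseline, with the pain covariate: SE 0.157, 0.177, 0.192 at week 13 over the three cases. The variance is only 2–3% below pain-only. At week 26 the SEs are 0.241, 0.243, 0.241; own-baseline adjustment then ranges from 12% more variance to 26% less.
- Central slope SE: 0.0096 with separate arm means, about 0.009 with a common mean and a linear trend through week 0, and 0.0124 with own baseline as covariate.

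**The case against.** The strongest reply is that the large gains concern contrasts the SAP does not define. It names no difference at week 13, 26 or 52. With time counted in weeks since baseline, the group coefficient is the arm difference at time zero, and the interaction, which carries the divergence between arms, gains nothing. That stands as a limit: the benefit is realised only if a follow-up time is named. But group is listed as a primary term, and a slope alone does not tell a reader how far apart the arms are.

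Second, week 0 may be a response, or the sentence may be shorthand for each outcome's own baseline, or the selection by information criteria may have changed the covariates. All are possible. The SAP states none of them, and the literal reading is pain.

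Third, the size rests on assumptions. If all correlations fall by 20% per 26 weeks, the central week-26 cut (1–6 surveys) drops from 23% to 12%, and the week-52 range (1–12 surveys) from 10–41% to about 3–11%. If r = q = 0.5, replacing baseline pain by own baseline gains nothing; adding own baseline and keeping pain still cuts week-13 variance by about 21%. The 86 is also the number enrolled; the analysed number may be smaller. These points shrink the gain but do not reverse it while week 0 is not a response.

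**Conclusion.** The concern holds, within its stated condition. As written, six of the eight models omit the outcome's own baseline, although a pre-assignment survey is required of everyone analysed. If week 0 is not a response, own-baseline adjustment lowers the variance of the arm difference by 18–58% at week 13 and 9–37% at week 26 with 1–6 surveys, and by 10–41% at week 52 with 1–12 surveys. For the group coefficient at the time origin the cut is 10–44% (1–6 surveys). These are variance ratios, so the Bonferroni multiplier does not alter them.

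The figures assume own-baseline correlations of 0.5–0.7, pain correlations of 0.2–0.4, and no decay over time. The comparison stays unbiased under randomisation, and the group-by-time inference is essentially unchanged. It is a worthwhile, inexpensive improvement, not a fault in validity.

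**What to change.** State in the SAP which of these is used:

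- **A.** Each model includes the baseline value of its own dependent variable as a covariate (baseline worst pain for the worst-pain model). Baseline average pain may be kept as an additional covariate.
- **B.** Week 0 is kept as a response, with one common baseline mean for both arms.

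With either, report the adjusted between-arm difference at a named follow-up time beside the group-by-time term.

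The cost is SAP wording and a re-run on data in hand, with one extra parameter per model under A if baseline pain is kept. Under A, participants lacking that PROMIS baseline leave the model. The break-even loss is 86 × (1 − variance ratio), assuming equal loss across arms and 1–6 surveys: at week 13, 15.5 patients in the weakest case and 35.8 in the central case; at week 26, 7.4 and 19.6.

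If week 0 is already a response with separate arm means, moving to A would widen the central slope SE from 0.0096 to 0.0124 SD per week. B with a linear trend through week 0 avoids this, but assumes the arms diverge linearly from baseline.

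The SAP is written in the past tense. If results have been seen, the re-run should be labelled a sensitivity analysis.

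### Baseline pain is named only as a covariate, which does not adjust the group-by-weeks contrast, and the PROMIS models name no adjustment for their own baseline

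*SAP*

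**What the plan says.** All of this is in the SAP, Statistical Analysis.

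- **Terms used to judge the drugs:** "The primary independent variables were medication group (desipramine vs. duloxetine) and its interaction with time (weeks since baseline) to assess differential treatment effects".
- **Baseline:** "Baseline pain intensity was included as a covariate". No interaction of baseline with time is mentioned.
- **Correlation structure:** "A random intercept for each participant accounted for within-subject correlations".
- **Model choice:** "Various model structures were evaluated using Akaike Information Criterion and Bayesian Information Criterion, with final models selected based on model fit and diagnostic assessments".
- **Outcomes:** "Dependent variables included pain intensity (average and worst), PROMIS Pain Interference, PROMIS Anxiety, PROMIS Depression, and PROMIS Physical Function". Baseline pain is the only baseline covariate named for any of them.
- **Baseline survey:** "The baseline assessment was defined as the most recent survey before treatment assignment". The SAP does not say whether this survey is also kept as a week-0 row of the response.
- **Size:** "we enrolled 38 patients in the desipramine group and 48 in the duloxetine group".

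The protocol specifies no model. Its Planned Enrollment section (6a) mentions correlation between repeated measures but gives no value.

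**The concern.** A reader who sees a baseline covariate will assume that the treatment comparison is protected against unequal starting pain. For the group term it is. For group by weeks it is not: in a random-intercept model that term is estimated from changes within patients, and a quantity that is constant within a patient shifts the patient's level but not the slope.

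Patients who start high tend to drift back towards the mean. If one small arm happens to start higher, that drift can look like a faster response to its drug. At stake are the credibility of a slope difference, given whatever imbalance arose, and some precision that data already held could recover.

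The PROMIS outcomes are less protected still. Their models name baseline pain, which is only a proxy for baseline depression, anxiety, interference or function.

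**Working it through.** **1. The plan's own figures.** Inputs from the SAP: SD 2.25, alpha 0.05 (two-sided assumed), 38 and 48 patients.

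- Planned size: 2 × (1.960 + 1.282)² × 2.25² / 1² = 106.4, so 107 per group, as stated.
- SE of a difference in means: 2.25 × √(1/38 + 1/48) = 0.489.
- Detectable difference: 0.489 × (1.960 + 0.842) = 1.37 at 80% power and 0.489 × (1.960 + 1.282) = 1.58 at 90%, as stated.

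If baseline pain has the same SD, a chance baseline difference also has SE 0.489 and a 95% range of ±1.96 × 0.489 = ±0.96 NRS.

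**2. Does a baseline main effect change group by weeks?** Random-intercept models were fitted to simulated trials of 86 patients.

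- Six complete monthly surveys, one data set: group by time was 0.06101 (SE 0.06151) both with and without the baseline main effect.
- With 30% of surveys missing, one data set: 0.25116 without baseline, 0.25290 with the main effect, 0.22575 with baseline by time.
- Averages over 25 simulated trials in each of four complete-data settings: unchanged to three decimals by the main effect (for example −0.145 and −0.145). With 40% of follow-up surveys missing at random, it moved by at most about 0.025.

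**3. How much imbalance reaches the slope?** With complete visits the group-by-weeks estimate is the difference in mean within-patient least-squares slopes. With no drug effect, equal variances, and a baseline difference d₀, the expected slope difference is d₀ × Σ wₜ rₜ. Here wₜ = (t − t̄)/Σ(t − t̄)² and rₜ is the correlation of the week-t score with baseline (1 at week 0).

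Worked case: week 0 kept as a response, visits every 4 weeks to week 24, constant correlation 0.5.

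- t̄ = 12 and Σ(t − t̄)² = 448, so w₀ = −12/448 = −0.0268.
- The weights sum to zero, so Σ wₜ rₜ = w₀ × (1 − 0.5) = −0.0134 per week.
- Over 24 weeks: −0.32 NRS per 1 NRS of imbalance, or −0.157 for d₀ = 0.489.

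With post-baseline rows only and constant correlation, Σ wₜ rₜ = 0 exactly.

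The table gives the size of the spurious drug difference, in NRS, by the end of follow-up for a 1-SE imbalance. All correlations are assumptions. Falling correlations start at the value shown at week 4 and decay towards 0.3.

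| Rows modelled | Correlation with baseline | Follow-up to week 24 | Follow-up to week 52 |
|---|---|---|---|
| Post-baseline only | constant | 0 | 0 |
| Post-baseline only | 0.5, falling | 0.09 | 0.09 |
| Post-baseline only | 0.7, falling | 0.19 | 0.18 |
| Week 0 also a response | constant 0.3 | 0.22 | 0.13 |
| Week 0 also a response | constant 0.5 | 0.16 | 0.09 |
| Week 0 also a response | constant 0.7 | 0.09 | 0.05 |
| Week 0 also a response | 0.5, falling | 0.25 | 0.19 |
| Week 0 also a response | 0.7, falling | 0.27 | 0.25 |

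A different set of assumed structures was also tried: stable variance share 30–60%, decaying share 10–50% with monthly autocorrelation 0.7–0.9, noise 20–30%. Per 1 NRS of imbalance these gave 0.04–0.37 with post-baseline rows and 0.19–0.51 with week 0 as a response. Multiplied by 0.489, that is 0.02–0.18 and 0.09–0.25.

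**4. Error rate and precision.** 20,000 simulated null trials per setting, 38 against 48 patients, monthly visits to week 24.

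- *Week 0 a response, constant correlation 0.5:* type I error without baseline by time was 4.8% overall, 7.2% when the imbalance exceeded 0.49 and 10.9% when it exceeded 0.8. With the term it was 3.5%, 3.3% and 3.1%.
- *Post-baseline rows, constant correlation 0.5:* 5.2%, 5.4% and 5.3% without the term, so nothing to repair.
- *Variance of the slope contrast removed by the term,* from the simulated SDs over 24 weeks: constant correlation, post-baseline rows, 0.498 to 0.500 (none); falling correlation, post-baseline rows, 1 − (0.610/0.634)² = 7%; constant correlation, week 0 included, 1 − (0.360/0.388)² = 14%; falling correlation, week 0 included, 1 − (0.464/0.537)² = 25%.

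**The case against.** The strongest reply is that the SAP's own structure implies no leak. A random intercept means constant correlation. With post-baseline rows only, the contamination is then exactly zero. This stands, and it is why the point is conditional. But the SAP does not say that the baseline survey is kept out of the response, and constant correlation over as much as 52 weeks is an assumption.

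Three stronger readings are tempting, and the documents support none of them.

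- *The plan rules out a baseline-by-time term.* A main effect is the ordinary reading, since an interaction is named for group and none for baseline. But structures were compared by AIC and BIC, so such a term is neither stated nor excluded.
- *The baseline adjustment achieves nothing.* Medication group is itself one of the primary terms, and the covariate does adjust it.
- *The trial's slope result is biased.* No baseline pain values by arm are given, so no imbalance is documented. Averaged over randomisation there is no overall bias, and the overall type I error was 4.8% even with week 0 as a response under constant correlation. That defence is a little weaker here than in a fully analysed trial, because participants without follow-up surveys are excluded.

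It is also fair to say that the random-intercept-only covariance matters more if correlation decays. In those simulations type I error for group by time was 16–18% without baseline by time and still 14–15% with it. That is a separate fault. It limits what this fix achieves but does not remove the reason for it.

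**Conclusion.** The point holds in a limited form. As ordinarily read, the baseline covariate does not adjust the group-by-weeks contrast, and the PROMIS models state no adjustment for their own baseline. Imbalance can reach the slope contrast under either of two conditions that the SAP leaves open: a week-0 response row, or decaying correlation with baseline.

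For a 1-SE imbalance of 0.49 NRS the effect is roughly 0 to 0.25 NRS by the end of follow-up (0.27 in the most extreme case tried). That is less than a fifth of the smaller detectable difference (0.27/1.37 = 0.20), which is only a yardstick because it was computed for a difference in means rather than in slopes. The precision to be gained runs from nothing to about a quarter of the slope variance, and at the upper end only if week 0 is also a response.

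These sizes rest on assumed correlations, equal variances, 4-weekly surveys and linear time. The improvement is worth making, but its size is modest.

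**What to change.** - In each model, adjust for that outcome's own baseline score and add its interaction with weeks (with visit, if time is categorical). Keep both terms whatever AIC or BIC indicates.
- State whether the baseline survey is a covariate or a week-0 response, and do not use it as both. A constrained longitudinal model with a common baseline mean is an acceptable alternative.
- The SAP reports the models as already selected, so label the change as a revision or a sensitivity analysis and show it beside the existing results.

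The cost is a sentence or two in the SAP, one extra parameter per model and a re-run on data already held. The change does not correct any misspecification of the random-intercept-only covariance, which needs its own check.

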2. STUDY PROCEDURES

a. Procedures

Study Design: We will conduct a prospective open label randomized trial comparing effectiveness of duloxetine and desipramine.

Randomization (research): After obtaining research informed consent, the participants are going to be randomized by the treating pain provider using point of care randomization during the clinic visit. Point of care randomization will be done through Collaborative

Health Outcomes Information Registry (CHOIR) using computer generated random numbers.

Intervention: (standard of care) The participants are going to receive either duloxetine or desipramine. Duloxetine will be started at 20 mg per day. It will be increased to 40 mg per day at the beginning of week two, and then to 60 mg per day at the beginning of week three. Desipramine will be started at 25 mg per day. It will be increased to 50 mg per day at the beginning of week two, and then to 75 mg per day at the beginning of week three. These treatments will be continued for at least 6 months provided that the patients can tolerate the side effects and are willing to continue the treatment. Further titration of doses based on participants' tolerance and response is allowed based on clinical decision of the treating pain provider. Concomitant use of other analgesics or pain medications as well as pain interventions are also allowed.

Data collection: (standard of care and research) The participants are going to receive monthly electronic surveys which are already part of their routine clinical care. These surveys are going to be abbreviated to include average and worst Numerical Rating Scale (NRS) of pain; National Institute of Health (NIH) Patient Reported Outcomes Measurement Information System (PROMIS) measures for function, depression and pain interference; and questions about medication compliance, dose and adverse events. Data about use of other analgesics and medications, and pain interventions will also be recorded at these intervals from participants' electronic health records. If the participants do not complete the surveys within five days of receipt of the survey link, they will be contacted to be reminded of the survey. We will also record participants' baseline characteristics including age, sex, main pain diagnosis, other pain diagnoses, psychological comorbidities, medical comorbidities, medication use, and education.

b. Procedure Risks

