6. PARTICIPANT POPULATION

a. Planned Enrollment

Accepting type I error of 0.05 with 90% power, we will require 107 participants per group to detect one unit between-group difference in NRS pain scale. We are proposing a more conservative (larger) sample size to: (1) preserve power if the effect size is underestimated secondary to low medication adherence; and (2) preserve power for our subgroup analyses. We will therefore add 50% to our sample size to a total of 160 patients in each arm. Correlation between repeated measure will decrease variance and increase the power of the proposed study.

b. Age, Gender, and Ethnic Background

Men and women of any ethnic background who are 18 years old or above will be enrolled.

c. Vulnerable Populations

We will not enroll potentially vulnerable subjects.

d. Rationale for Exclusion of Certain Populations

We are studying the comparative effectiveness of these two medications in adults. Study of chronic pain in children is beyond the scope of our study.

e. Stanford Populations

Not applicable

f. Healthy Volunteers

Not applicable

g. Recruitment Details

All adult patients with chronic pain receiving care from Stanford Pain Management Center will be assessed for eligibility by their treating pain physician during each clinical visit. If eligible, the treating pain physician will go through the oral consent script. If the patient consents to participate, he/she will be randomized to receiving either duloxetine or desipramine. Open label prescription will be then sent to participants' pharmacy.

h. Eligibility Criteria

i. Inclusion Criteria

1. Age of 18 years old or above
2. Persistent pain for more than 3 months
3. Candidate for treatment by anti-depressant based on treating pain provider

ii. Exclusion Criteria

1. Prior failure of duloxetine and/or desipramine (patients who have failed other TCAs or SNRIs can be considered for the trial based on the reason for previous medication failure)
2. Contraindication to taking duloxetine or desipramine
3. Patient refusal

i. **Screening Procedures**

We do not collect any PHI prior to enrollment.

j. **Participation in Multiple Protocols**

Participants will be asked if they are enrolled in any other research study.

k. **Payments to Participants**

Participants will not receive any payment for taking part in this study.

l. **Costs to Participants**

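### The SAP's detectable difference of 1.37–1.58 assumes one two-sided test at 0.05, but its mixed models of eight unranked outcomes, NRS pain included, carry a Bonferroni correction of unstated family and size

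*SAP*

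**What the plan says.** **Power.** Protocol section 6.a sizes the trial on the NRS pain scale: "Accepting type I error of 0.05 with 90% power". The SAP (Statistical Analysis, opening paragraph) repeats that "107 participants per group would provide 90% power to detect a one-unit between-group difference in the NRS pain score", with SD 2.25. It then reports early stopping, gives the achieved numbers as "we enrolled 38 patients in the desipramine group and 48 in the duloxetine group", and concludes that "we could detect a difference of 1.37–1.58 in NRS pain reduction with 80–90% power". That last statement gives no alpha of its own. Neither document says whether the NRS score meant is average or worst pain.

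**Outcomes.** The SAP paragraph on longitudinal models lists eight dependent variables: average pain, worst pain, Pain Interference, and "PROMIS Anxiety, PROMIS Depression, and PROMIS Physical Function (Upper Extremity, Mobility, and Composite) scores". Each model has a medication-group term and a group-by-time term, both described as primary independent variables.

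**Multiplicity.** The same paragraph says "Bonferroni correction was applied to account for multiple comparisons". It gives no family, no number of tests and no adjusted alpha.

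**Ranking.** Neither document names a primary outcome. Protocol section 1.a lists four aims without ranking them. The SAP's term 'primary analysis' refers to the modified intention-to-treat approach, not to an endpoint.

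**The concern.** The power statement and the multiplicity rule sit in one plan but appear to assume different significance levels. The first treats NRS pain as the only test, at 0.05. The second divides alpha among several tests, in a paragraph where NRS pain appears twice in the outcome list.

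This matters most if the pain comparison is not significant. The trial enrolled 86 people, against 107 per group required by the calculation and 160 per arm planned in Protocol section 6.a. A reader told that a difference of 1.37–1.58 was detectable with 80–90% power may take a null result as good evidence against a difference of that size. If the test was run at a much smaller alpha, the result is weaker evidence than the stated power implies.

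**Working it through.** **Inputs.** SD 2.25, groups of 38 and 48, and the pairs 1.37 at 80% and 1.58 at 90% (SAP, opening paragraph); alpha 0.05 (SAP and Protocol section 6.a). Sidedness is not stated. Eight outcomes are counted from the SAP's list. The number of tests m is not stated, so every value of m below is an assumption.

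**Step 1: reproduce the plan's figures.**
- Original size: n per group = 2 × (1.960 + 1.282)² × 2.25² / 1² = 106.4, rounded up to 107. This matches.
- Standard error with the achieved groups: SE = 2.25 × √(1/38 + 1/48) = 0.4886.
- Detectable difference = (z for two-sided alpha + z for power) × SE. At 0.05 this is (1.960 + 0.842) × 0.4886 = 1.369 for 80% power and (1.960 + 1.282) × 0.4886 = 1.584 for 90%. Both match.
- One-sided 0.05 gives 1.21–1.43, which does not match. A noncentral-t version at two-sided 0.05 gives 1.38–1.60.

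The stated range is therefore a comparison of two means at two-sided 0.05 with no multiplicity adjustment.

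**Step 2: apply Bonferroni.** With m tests, alpha is 0.05/m, and power at a difference d is approximately Φ(d/SE − z for two-sided alpha). For m = 8, alpha = 0.00625 and z = 2.734:
- power at 1.37: Φ(2.804 − 2.734) = 52.8%
- power at 1.58: Φ(3.234 − 2.734) = 69.1%
- detectable difference: (2.734 + 0.842) × 0.4886 = 1.747 for 80% and (2.734 + 1.282) × 0.4886 = 1.962 for 90%

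| Assumed m | Alpha per test | Power at 1.37 | Power at 1.58 | Detectable at 80% | Detectable at 90% |
|---|---|---|---|---|---|
| 1 (as stated) | 0.05 | 80.1% | 89.9% | 1.37 | 1.58 |
| 2 | 0.025 | 71.3% | 84.0% | 1.51 | 1.72 |
| 4 | 0.0125 | 62.0% | 76.9% | 1.63 | 1.85 |
| 8 (one test per outcome) | 0.00625 | 52.8% | 69.1% | 1.75 | 1.96 |
| 16 (group and group-by-time for each) | 0.003125 | 44.0% | 61.0% | 1.85 | 2.07 |

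The noncentral-t version at m = 8 gives 50.3% and 66.6%, so the normal approximation is not what drives the result.

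**Step 3: how strict is Bonferroni here?** Suppose the eight test statistics are equally correlated at 0.5, 0.7 or 0.9. These values are assumed, as the documents give none. Simulation then puts the true familywise error at about 4.0%, 3.1% or 1.9% instead of 5%. Plain Bonferroni is conservative when outcomes overlap.

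**The case against.** **The family of eight is not in the text.** The Bonferroni sentence follows remarks on model selection and diagnostics. It could cover terms or contrasts within a model, the eight outcomes, or all sixteen tests. This stands: a reader might infer that NRS pain is tested at 0.00625, but the SAP does not say so. The inconsistency does not depend on m = 8, however. Any family of two or more that contains NRS pain breaks the stated power, and if NRS pain is exempt the SAP has to say that.

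**The calculation is not for the planned analysis.** The SAP fits a baseline-adjusted repeated-measures model, and Protocol section 6.a expects correlation between repeated measures to raise power. Power for a group-by-time slope would differ again. This also stands, and no correlations are given to settle it. But the SAP itself presents the two-means figure as what the trial could detect, so that figure should at least use the alpha applied. In the other direction, 38 and 48 are described as enrolled, and the SAP excludes people without follow-up surveys. If any of the 86 were dropped, all the figures above are slightly too favourable.

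**Bonferroni is valid, so Holm is a preference.** Bonferroni is valid, and the gain from Holm depends on correlations and effects that the documents do not give. Holm nevertheless has the same familywise guarantee and rejects everything Bonferroni rejects.

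**Stronger readings that the documents do not support.**
- That the correction removes the trial's power. At m = 8 it lowers the stated power by about 27 points at 1.37 and 21 points at 1.58.
- That the Composite in "PROMIS Physical Function (Upper Extremity, Mobility, and Composite) scores" is known to be built from the other two scores. That is a reasonable inference from the names, but it is not stated.
- That Anxiety was improperly added. The protocol's survey lists PROMIS "measures for function, depression and pain interference" and omits it, but the SAP also draws on clinical surveys, which may be its source.
- That average NRS should simply be declared sole primary and other scores demoted. The SAP was revised after the study stopped, so this would be a debatable post hoc choice, and it would leave open whether the group or the group-by-time term is the test.

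**Conclusion.** The concern holds in a limited form. The 1.37–1.58 range is correct arithmetic for one two-sided test at 0.05, but the SAP does not establish that NRS pain is tested that way, and its multiplicity sentence suggests otherwise.

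On the natural but assumed reading that the eight outcomes form the family, the difference detectable with 80–90% power is 1.75–1.96. The range over two to sixteen tests is from 1.51–1.72 to 1.85–2.07. For the one-point difference on which the trial was first sized, 38 versus 48 gives 53.5% power at 0.05 and 24.6% at 0.00625.

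All these sizes rest on SD 2.25, the enrolled counts and a plain comparison of two means. They show how far the SAP's own statement shifts with the alpha used. They do not estimate the power of the mixed model.

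**What to change.** 1. State which tests the correction covers (outcomes, model terms or both) and how many there are.
2. Restate the detectable NRS difference at the alpha that NRS pain actually receives: 1.75–1.96 if there are eight tests, otherwise the matching row of the table. Say that it is a two-means approximation.
3. Use Holm in place of plain Bonferroni. Familywise control is unchanged and no rejection is lost. Since Holm's first step uses 0.05/m, the restated difference remains the safe figure to quote; Holm does not by itself bring back 1.37–1.58.
4. If NRS pain is instead to be tested alone at 0.05 as the sample-size outcome, name the score (average or worst) and the single contrast (group or group-by-time), and label the choice as specified after the study stopped. Only then would the existing range match the alpha used.

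**Cost.** SAP wording and recalculated adjusted p-values; no new data. The quoted detectable difference becomes less favourable unless item 4 is taken, and any change of error control after stopping has to be disclosed.
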